Consistent with the purposes described above, this information may be transmitted to the Sponsor, and subsidiaries, affiliates and agents of the Sponsor, in your country and other countries, including countries that do not have laws protecting such information. Additionally, the investigator's name and business contact information may be included when reporting certain serious adverse events to regulatory agencies or to other investigators. By signing this protocol, the investigator expressly consents to these uses and disclosures.

If this is a multicenter study, in order to facilitate contact between investigators, the Sponsor may share an investigator's name and contact information with other participating investigators upon request.

Administrative:

Compliance with Financial Disclosure Requirements

Financial Disclosure requirements are outlined in the US Food and Drug Administration Regulations, Financial Disclosure by Clinical Investigators (21 CFR Part 54). It is the Sponsor's responsibility to determine, based on these regulations, whether a request for Financial Disclosure information is required. It is the investigator's/subinvestigator's responsibility to comply with any such request.

The investigator/subinvestigator(s) agree, if requested by the Sponsor in accordance with 21 CFR Part 54, to provide his/her financial interests in and/or arrangements with the Sponsor to allow for the submission of complete and accurate certification and disclosure statements. The investigator/subinvestigator(s) further agree to provide this information on a Certification/Disclosure Form, commonly known as a financial disclosure form, provided by the Sponsor or through a secure password-protected electronic portal provided by the Sponsor. The investigator/subinvestigator(s) also consent to the transmission of this information to the Sponsor in the United States for these purposes. This may involve the transmission of information to countries that do not have laws protecting personal data.

Compliance with Law, Audit and Debarment

By signing this protocol, the investigator agrees to conduct the study in an efficient and diligent manner and in conformance with this protocol; generally accepted standards of Good Pharmacoepidemiology Practice and all applicable federal, state and local laws, rules and regulations relating to the conduct of the study.

The investigator also agrees to allow monitoring, audits, Institutional Review Board/Independent Ethics Committee review and regulatory agency inspection of study-related documents and procedures and provide for direct access to all study-related source data and documents.

The investigator agrees not to seek reimbursement from subjects, their insurance providers or from government programs for procedures included as part of the study reimbursed to the investigator by the Sponsor.

The Investigator shall prepare and maintain complete and accurate study documentation in compliance with Good Pharmacoepidemiology Practice, standards and applicable federal, state and local laws, rules and regulations; and, for each subject participating in the study, provide all data, and, upon completion or termination of the study, submit any other reports to the Sponsor as required by this protocol or as otherwise required pursuant to any agreement with the Sponsor.

Study documentation will be promptly and fully disclosed to the Sponsor by the investigator upon request and also shall be made available at the investigator's site upon request for inspection, copying, review and audit at reasonable times by representatives of the Sponsor or any regulatory agencies. The investigator agrees to promptly take any reasonable steps that are requested by the Sponsor as a result of an audit to cure deficiencies in the study documentation and worksheets/case report forms.

The investigator must maintain copies of all documentation and records relating to the conduct of the study in accordance with their institution's records retention schedule which is compliant with all applicable regional and national laws and regulatory requirements. If an institution does not have a records retention schedule to manage its records long-term, the investigator must maintain all documentation and records relating to the conduct of the study for 5 years after final report or first publication of study results, whichever comes later, per GPP guidelines. This documentation includes, but is not limited to, the protocol, worksheets/case report forms, advertising for subject participation, adverse event reports, subject source data, correspondence with regulatory authorities and IRBs/ERCs, consent forms, investigator's curricula vitae, monitor visit logs, laboratory reference ranges, laboratory certification or quality control procedures and laboratory director curriculum vitae. All study documents shall be made available if required by relevant regulatory authorities. The investigator must consult with the Sponsor prior to discarding study and/or subject files.

The investigator will promptly inform the Sponsor of any regulatory agency inspection conducted for this study.

Persons debarred from conducting or working on studies by any court or regulatory agency will not be allowed to conduct or work on this Sponsor's studies. The investigator will immediately disclose in writing to the Sponsor if any person who is involved in conducting the study is debarred or if any proceeding for debarment is pending or, to the best of the investigator's knowledge, threatened.

In the event the Sponsor prematurely terminates a particular study site, the Sponsor will promptly notify that site's IRB/IEC.

According to European legislation, a Sponsor must designate an overall coordinating investigator for a multi-center study (including multinational). When more than one study site is open in an EU country, Merck, as the Sponsor, will designate, per country, a national principal coordinator (Protocol CI), responsible for coordinating the work of the principal investigators at the different sites in that Member State, according to national regulations. For a single-center study, the Protocol CI is the principal investigator. In addition, the Sponsor must designate a principal or coordinating investigator to review the study report that summarizes the study results and confirm that, to the best of his/her knowledge, the report accurately describes the conduct and results of the study in the study's final report. The Sponsor may consider one or more factors in the selection of the individual to serve as the Protocol CI and or CSR CI (e.g., availability of the CI during the anticipated review process, thorough understanding of study methods, appropriate enrollment of subject cohort, timely achievement of study milestones). The Protocol CI must be a participating study investigator.

Compliance with Study Registration and Results Posting Requirements

Under the terms of the Food and Drug Administration Modernization Act (FDAMA) and the Food and Drug Administration Amendments Act (FDAAA), the Sponsor of the study is solely responsible for determining whether the study and its results are subject to the requirements for submission to the Clinical Trials Data Bank, such as ENCePP. Merck, as Sponsor of this study, will review this protocol and submit the information necessary to fulfill these requirements. Merck entries are not limited to FDAMA/FDAAA mandated studies. Information posted will allow subjects to identify potentially appropriate studies for their disease conditions and pursue participation by calling a central contact number for further information on appropriate study locations and site contact information.

By signing this protocol, the investigator acknowledges that the statutory obligations under FDAMA/FDAAA are that of the Sponsor and agrees not to submit any information about this study or its results to the Clinical Trials Data Bank.

12.5 Annex 5 About Desloratidine

Aerius, Azomyr, and NeoClarityn in the EU, and in the rest of the world as, Claramax, Clarinex, Larinex, Dazit, Deselex, and Delot. It is an active metabolite of Loratadine, which is also on the market.

DL is available as tablets (including orally disintegrating and extended release) and as syrup.

DL is a second-generation H1-antagonist. It is a tricyclic antihistamine, which has a selective and peripheral H1-antagonist action. It is an antagonist at histamine H1 receptors, and an antagonist at all subtypes of the muscarinic acetylcholine receptor. It has a long-lasting effect, and in moderate and low doses, does not cause drowsiness because it does not readily enter the central nervous system.

Unlike other antihistamines, DL is also effective in relieving nasal congestion, particularly in patients with allergic rhinitis.

Most common side-effects are fatigue, dry mouth, headache, and gastrointestinal disturbances.

In the EU, DL is a prescription drug approved for the relief of symptoms associated with allergic rhinitis and urticaria in both adults and children. The Anatomical Therapeutic Classification (ATC) code for DL is R06AX27.

Table 9 Overview of DL formulations in the Nordic countries. Dates of approval are identical for all EU countries.

Formulation	Date of approval
Film coated tablet, 5 mg	15 January 2001
Orodispersible tablet, 2.5 mg	23 April 2007
Orodispersible tablet, 5.0 mg	23 April 2007
Oral solution, 0.5 mg/ml	23 April 200

12.6 Annex 6 ICD-10 Codes and ATC Codes

Diagnosis/drugs to be identified in registers	Proposed classification system	Proposed codes by clinicians
Acute drug intoxication and overdose of drugs	ICD-10	T88.6 T88.7 T36 T50
Antiepileptic medicine	ATC	N03A N05BA
Asthma	ICD-10	J45
	ATC	R03A and R03B
Atrial fibrillation or flutter	ICD-10	I48
Brain Tumor (both malignant and benign)	ICD-10	C70 and C71 D33
Chronic urticaria	ICD-10	L50 (excluding acute urticaria: L50.8D) L56.3
Congenital pre-excitation syndrome	ICD-10	I45.6
Desloratadine	ATC	R06AX27
Epilepsy	ICD-10	G40
Head trauma	ICD-10	S06
Loratadine	ATC	R06AX13
Malignant brain tumor	ICD-10	C70 and C71
Seizure	ICD-10	R56
Severe rhinitis (immunotherapy)	ATC	V01AA (excluding V01AA07)
Stroke (all types)	ICD-10	I61 I62 I63 I64.9
Supraventricular arrhythmias	ICD-10	I47.1

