5 RATIONALE AND BACKGROUND

Since market authorization, there have been a small number of adverse event reports of seizures and supraventricular arrhythmias in patients taking desloratadine (DL), but the case reports do not permit evaluation of the association. Denmark, Finland, Norway, and Sweden (hereafter also referred to as ‘Nordic countries’) offer unique opportunities for such a study by means of the existence of centralized registration of activities in the healthcare sector, covering complete populations over many years.

The European Medicines Agency (EMA) had previously requested that Merck Sharp and Dohme (MSD) consider options for a post-authorization safety study (PASS; Category 3 PV activity) to investigate whether there is an association between desloratadine (DL) use and seizures, supraventricular tachycardia, and atrial fibrillation or flutter in the general population. This PASS (P203) was submitted and the regulatory commitment was accepted as complete using data from Denmark, Finland, and Sweden in January 2020. Although the original commitment and its associated protocol (P203) included analyses on four countries, the data for Norway were very delayed and the EMA subsequently allowed MSD to provide a final report without these data.

This protocol (P205) is a voluntary PASS including analyses as intended in the original study protocol (P203) of the Norway data both alone and in combination with the original three countries. The findings for the analyses for all four countries (P205) will be submitted to the EU health authorities with the next PSUR. The only change from the original protocol’s (P203) study methods/design is the removal of the secondary analyses. The subsequent final report for this protocol (P205) will build upon the report with the three countries to be inclusive of all four as was the intent of the original PASS.

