7.3.2 Outcomes

Three outcome variables will be used in the present study: first seizure (Substudy 2B), first SVT (Substudy 3B), and first A-fib/flu (Substudy 4B). Except where noted, the case definition of seizure excludes febrile seizure, a condition in infancy and early childhood attributed to fever. However, supplementary analysis 2 will evaluate the outcomes of febrile and non-febrile seizures in children. (The diagnosis of febrile seizure is generally not used in adults.) Information on outcome variables will be obtained from the Nordic national patient registers, including diagnostic and treatment information for patients treated at the secondary and tertiary hospital level in all four Nordic countries using International Classification of Diseases (ICD)- 10 codes. We will exclude seizure cases if they are registered with brain tumor (benign and malignant), stroke, or acute drug intoxication or overdose of drugs during the same hospitalization as the seizure. [Table 2](#) gives an overview of the outcome variables in the study. For all outcome variables, we will include the primary diagnoses from the emergency room or inpatient settings registered in the Nordic national patient registers.

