In Substudy 2B, seizure outcomes for which a drug overdose is also registered at the same hospitalization are excluded. In general, drug overdoses are likely to be underreported in the registries, as the registries often do not have sufficient detail to differentiate between overdoses from different types of drugs. Therefore, it is not possible to distinguish between overdoses from DL and overdoses from other drugs. Because overdoses of DL are rare compared to other drug overdoses, persons with any drug overdose registered during the same hospitalization as the seizure are excluded from analysis 2B. As a result, this study cannot determine whether the seizure outcomes are specifically associated with DL overdoses.

Sample size

Based on the assumptions made, the sample size is not adequate in the youngest age group for the assessment of the potential association between DL use and A-fib. Also, in this age group only relatively strong associations (IRR=8.2) can be properly assessed for the association between DL use and SVT.

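### Annex 6 files two adverse-drug-effect codes (T88.6, T88.7) under overdose, so first seizures that also carry such a code are excluded, which can bias the seizure IRR toward 1

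*Protocol*

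**What the plan says.** Protocol section 7.3.2 removes a seizure case if the register shows "acute drug intoxication or overdose of drugs during the same hospitalization as the seizure". Section 7.9 repeats the rule for Substudy 2B: "persons with any drug overdose registered during the same hospitalization as the seizure are excluded from analysis 2B".

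Annex 6 supplies the codes. The row labelled "Acute drug intoxication and overdose of drugs" reads "T88.6 T88.7 T36 T50".

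Section 7.9 gives the reason. Overdoses are under-reported, "it is not possible to distinguish between overdoses from DL and overdoses from other drugs", and overdoses of desloratadine (DL) are said to be rare compared with other overdoses. The only consequence it admits is that "this study cannot determine whether the seizure outcomes are specifically associated with DL overdoses".

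Sections 7.3.2 and 7.9 also say that only primary diagnoses count as outcomes. None of the supplementary analyses listed in section 7.7.5 brings the excluded seizures back.

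**The concern.** The label and two of the codes under it do not match. Overdose is a reason to set a seizure aside, because the study is not about overdose. A suspected adverse effect at ordinary use is different. Section 5 says the study was prompted by adverse event reports in DL users, and it cites four children with seizures described as induced by DL.

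A filter triggered by suspected drug causation is not neutral between exposed and unexposed time. DL is most readily suspected while it is being taken. If DL causes seizures and some of them receive T88.6 or T88.7, those cases leave the exposed numerator and the IRR moves toward 1. In a safety study that is the direction of false reassurance, and neither the rationale nor the limitations section tells the reader about it.

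**Working it through.** **1. The codes.** Annex 6 lists the codes without defining them. Their meaning comes from ICD-10, which the annex names as the classification:
- T88.6: anaphylactic shock due to an adverse effect of a correct drug properly administered.
- T88.7: unspecified adverse effect of a drug.
- T36 and T50 (probably a range whose dash was lost in text extraction): poisoning by drugs.

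Only the last item fits the label.

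**2. Which seizures are lost.** Two conditions must hold together: R56 is the primary diagnosis, and T88.6 or T88.7 is registered in the same hospitalization. A seizure coded R56 alone stays in. If the adverse-effect code is primary, the seizure fails the primary-diagnosis rule whatever Annex 6 says.

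**3. The plan's own figure.** The Annex 7 equation, with p2 = 1 − exp(−p2′t), one-sided α = 0.05 and 80% power, was solved for the four seizure rows of Table 6. It gives minimum detectable IRRs of 3.00, 1.45, 1.30 and 1.68 (stated: 3.0, 1.5, 1.3, 1.7). For ages 0–4 the inputs are n = 20,000, E = 10/52, 65 per 100,000 and t = 2. The formula then expects about 5 exposed cases at IRR 1 and about 15 at IRR 3.0, an excess of about 10.

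**4. Effect of the exclusion.** Set the unexposed rate to 1. The exposed rate is then 1 (background) plus IRR − 1 (caused by DL). If a share f of the DL-caused seizures is dropped and nothing else is lost:

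observed IRR = 1 + (IRR − 1)(1 − f)

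The documents give no f, so the values below are assumptions.

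| True IRR | f = 10% | f = 25% | f = 50% |
|---|---|---|---|
| 1.3 | 1.27 | 1.23 | 1.15 |
| 1.5 | 1.45 | 1.38 | 1.25 |
| 3.0 | 2.8 | 2.5 | 2.0 |

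For example, 1 + 0.5 × 0.75 = 1.375. At ages 0–4 with a true IRR of 3.0, power under the Annex 7 set-up falls from 80% to 75%, 65% and 44%. In cases, that is 1, 2.5 or 5 of the roughly 10 excess seizures.

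**5. Offset from unexposed time.** The codes are not specific to DL. If a share g of background seizures carries them in both periods:

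observed IRR = [(1 − g) + (IRR − 1)(1 − f)] / (1 − g) = 1 + (IRR − 1)(1 − f)/(1 − g)

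For IRR = 1.5, f = 25% and an assumed g of 5%, this is 1 + 0.5 × 0.75/0.95 = 1.39 instead of 1.38. At g = f there is no bias. The pull toward 1 requires f > g, which is what one expects if the code reflects suspected drug causation.

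**The case against.** **Code meanings.** The protocol does not print what T88.6 and T88.7 mean. That is true, but the protocol prescribes ICD-10, and the meaning of a listed code is part of the instruction.

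**Scope.** A reader might infer that every seizure a clinician attributed to a drug is deleted. The documents do not support that: the loss is confined to primary R56 with one of the two codes in the same hospitalization.

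**Size.** A reader might also apply f to all exposed seizures, so that the observed IRR is IRR × (1 − f), and conclude that the detectable 1.3 of Table 6 vanishes at f = 23%. At a true IRR of 1.3 only 0.3/1.3 = 23% of exposed seizures are excess. If the coded cases are the DL-caused ones, f = 20% of all exposed seizures means that 0.20 × 1.3/0.3 = 87% of those were recognised and coded. At 1.5 it means 0.20 × 1.5/0.5 = 60%. Nothing in the protocol supports coding that complete, and section 7.9 expects overdose to be under-reported.

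**Exposed time only.** Nor do the documents show that unexposed seizures almost never carry these codes. Sections 7.3.1 and 7.9 accept that unexposed time may include loratadine, and they raise other antihistamines as a further possible source of misclassification.

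**Comparability.** Section 5 says P205 changes nothing from P203 except removing the secondary analyses, and the three-country results are already reported. Changing the case definition now departs from that. This objection stands, and it is why both versions should be reported.

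**Conclusion.** The mismatch is real and stands in the text: two adverse-effect codes sit under an overdose label, the exclusion uses them, and the stated rationale and limitation do not cover the result. The likely direction is toward an IRR of 1, assuming that DL causes some seizures and that these carry T88.6 or T88.7 more often than background seizures do.

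The size cannot be derived from the protocol. For assumed f of 10% to 50%, a true IRR of 1.5 is observed as 1.45 to 1.25 before any offset from unexposed time. If hardly any R56 admissions carry these codes, the effect is negligible. The case for acting does not rest on f being large: the study can count the affected seizures directly, and as written it would delete them without showing how many there were.

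**What to change.** - In Annex 6, take T88.6 and T88.7 out of the definition used to exclude seizure cases, and keep the poisoning codes.
- Tabulate first seizures with T88.6 or T88.7 in the same hospitalization by exposed and unexposed period. This replaces the assumed f and g with counts.
- Report the Substudy 2B IRR with and without these cases. P203 presumably used the same list (an inference from section 5), so the version that excludes them is the one comparable with the three-country report.
- While editing, reconcile section 7.3.2, which drops the seizure case, with section 7.9, which drops the person, and say what happens to that person's time at risk.

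The cost is a code-list edit, one table and a second run of one model. No further register variables should be needed, since the exclusion as written already requires these codes. The downsides are that a few seizures due to other drugs' adverse effects stay in the outcome, and that the case definition differs from the one presumably used in P203. The side-by-side result shows the effect of both.

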7.2.2 Exclusion criteria

Substudy 2A

- Individuals with a diagnosis of seizure, epilepsy, or prescriptions of antiepileptic medicine before entering the study period, as they have prevalent disease.
- Individuals with a diagnosis of malignant brain tumor or head trauma before the first seizure, as they are at high risk of seizures due to causes other than DL use.

Substudy 2B

- Individuals with a diagnosis of seizures, epilepsy, prescriptions of antiepileptic medicine, malignant brain tumor, or head trauma before redemption of first DL prescription, as they have prevalent disease or are at high risk of seizures due to causes other than DL use.
- Individuals with a brain tumor (benign and malignant), initiation of treatment with antiepileptic medicine, or head trauma occurring after beginning of DL use will be censored at date of first occurrence, as they are at high risk of seizures due to causes other than DL use.

Substudies 3A and 4A

- Individuals with a diagnosis of SVT or A-fib/flu before entering the study period, as they have prevalent disease.
- Individuals with a diagnosis of congenital pre-excitation syndrome (e.g., Wolff Parkinson White) before entering the study period, as they are at high risk of cardiac SVT or A-fib/flu due to causes other than DL use.

Substudies 3B and 4B

- Individuals with a diagnosis of SVT or A-fib/flu before use of DL, as they have prevalent disease.
- Individuals with a diagnosis of congenital pre-excitation syndrome (e.g., Wolff Parkinson White) before use of DL, as they are at high risk of SVT or A-fib/flu due to causes other than DL.

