Comorbidity	
Could be measured as history of hospital admissions or as an index (e.g., the Charlson index).
 
Comment (MSD): This is a non-specific indicator. Really a proxy for something else. Should be specified what part of comorbidity on top of the other indicators discussed should be included. Specific comorbidities are better.
 
Comment (expert): Agree that Charlson should not be used.
 
Conclusion: Do not include comorbidity index, number of admissions, or number of hospital contacts.
	Not relevant
Smoking	Smoking has an effect on seizures, COPD, asthmatic status, stroke, and metastatic cancer.	There is a directed path from smoking to: Metastatic cancer Seizures Stroke Asthmatic status COPD
Metastatic cancer	Metastatic cancer can increase risk of seizures.	There is a directed path from metastatic cancer to: Seizures
Use of other drugs	
Comment (MSD): Most drugs are not associated with seizures at normal doses. In addition, this would be extremely difficult to operationalize.
 
Drug-drug interactions have been shown but these interactions are generally very small.
 
It is more probable that high drug doses may influence high use of other drugs.
 
Conclusion: Do not include use of other drugs.
	Not relevant

Potential confounders	Discussion	List of directed paths (head-to-tail arrows)
Drug overdose (of drugs other than DL)	
Overdose of drugs other than DL affects the risk of seizures.
 
Comment (MSD): One of the most common reasons of new seizures is overdose of alcohol and cocaine.
 
The coding of overdose and the reason for overdose is not easily found in register studies.
 
May be too complicated to operationalize.
 
Comment (expert): Not specific enough codes for what kind of drug overdoses. Suggests using all drug overdoses as one variable (binary).
 
Comment (expert): Very unreliable information in the registers.
 
Persons with code for overdose (alcohol, drug, others) will probably be reliable, but there will be underreporting and it is difficult to differentiate between different types of overdose.
 
Comment (MSD): The problem gets very messy, because drug overdose due to DL is part of this group and we may not be able to separate this specific group.
 
Conclusion: Combine any overdose as one binary variable.
	
There is a directed path from drug overdose of drugs other than DL to:
 
Seizures

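### The Annex 6 code list for benign and malignant brain tumours omits benign meningeal tumours (D32), so it does not fully carry out the Substudy 2B censoring and same-hospitalization rules

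*Protocol*

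**What the plan says.** Three rules in the protocol use a brain-tumour definition for the seizure analysis, and they do not all use the same one.

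- **Baseline exclusion, 2B (section 7.2.2):** "Individuals with a diagnosis of seizures, epilepsy, prescriptions of antiepileptic medicine, malignant brain tumor, or head trauma before redemption of first DL prescription". Only malignant tumours are named. The 2A exclusion is also limited to malignant tumours.
- **Censoring, 2B (section 7.2.2):** "Individuals with a brain tumor (benign and malignant), initiation of treatment with antiepileptic medicine". Once DL use has started, these patients, like those with a later head injury, leave follow-up at the first such event. Benign and malignant tumours both count.
- **Case exclusion (section 7.3.2):** "We will exclude seizure cases if they are registered with brain tumor (benign and malignant), stroke, or acute drug intoxication or overdose". The rule looks within the hospital stay of the seizure. Again both kinds count.

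Annex 6 gives two rows. The combined malignant-and-benign row lists "C70 and C71 D33". The malignant row lists C70 and C71. Seizure is R56, and antiepileptic medicine is N03A and N05BA. D32 and C79.3 appear nowhere in the protocol.

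Table 10 in Annex 8 treats metastatic cancer as a separate factor and notes: "Metastatic cancer can increase risk of seizures". Table 3 places it in the seizure DAG but not in the selected adjustment set.

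**The concern.** The combined Annex 6 row takes in meningeal tumours when they are malignant (C70) but not when they are benign (D32), although its label and both rules that use it cover benign tumours. The list is therefore narrower than the rule it serves. Sections 7.3.2 and 7.3.3 send the reader to Annex 6 for codes, so the protocol itself fixes the list.

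The protocol justifies these rules by saying that such patients are at high risk of seizure for reasons other than DL. If their seizures stay in the outcome, they are events that DL did not cause, and they pull the rate ratio towards 1. In a safety study that is the unwelcome direction, because it weakens a real signal.

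**Working it through.** **1. What a D32 code does under each rule.** The meanings of D32 and C79.3 are those of ICD-10, the coding system that section 7.3.2 names; Annex 6 does not print them.

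| Rule | Annex 6 row | Tumours meant | D32 caught? |
|---|---|---|---|
| Baseline exclusion, 2A and 2B | Malignant (C70, C71) | Malignant only | No, and not intended |
| Censoring after DL start, 2B | Combined (C70, C71, D33) | Benign and malignant | No, though intended |
| Same-hospitalization case exclusion | Combined (C70, C71, D33) | Benign and malignant | No, though intended |

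The mismatch lies in the last two rows only.

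**2. Whether other rules close the gap.** Prior seizure, epilepsy or an antiepileptic prescription excludes a patient at baseline, and starting N03A or N05BA after DL censors. These catch some patients with meningeal tumours. They do not catch a tumour whose first sign is the seizure, since none of these events comes before it. The same-hospitalization rule covers that case, and it fails when the tumour is coded D32. The outcome is also limited to primary diagnoses, so a stay with the tumour as primary diagnosis is not an event. The uncaught case is R56 as primary diagnosis with D32 registered in the same stay, or a later R56 event in a patient who should have been censored at D32.

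**3. The protocol's own seizure figures, for scale.** Annex 7 formula, one-sided 5%, 80% power, Table 6 inputs:

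(p1 − p2)² = (Zα + Zβ)² [p1q1/(En) + p2q2/((1 − E)n)], with p2 = 1 − exp(−p2′t).

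Solving for p1/p2 gives 3.00, 1.45, 1.30 and 1.68 for ages 0–4, 5–19, 20–64 and 65 and over. Table 6 prints 3.0, 1.5, 1.3 and 1.7. The figures agree closely, and this point changes none of them.

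**4. Size of the dilution.** Let f be the share of counted seizures in reference time that come from uncaught tumours, with the same adjusted rate in exposed and reference time. If r is the reference rate, the exposed rate is r(1 − f)·IRR + r·f, so

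observed IRR = 1 + (IRR − 1)(1 − f).

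The documents give no value for f; 2% to 10% is an assumption.

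| True IRR | f = 2% | f = 5% | f = 10% |
|---|---|---|---|
| 1.0 | 1.000 | 1.000 | 1.000 |
| 1.3 | 1.294 | 1.285 | 1.270 |
| 1.5 | 1.490 | 1.475 | 1.450 |
| 1.7 | 1.686 | 1.665 | 1.630 |
| 3.0 | 2.960 | 2.900 | 2.800 |

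For example, 1 + 0.7 × 0.98 = 1.686 and 1 + 0.7 × 0.90 = 1.630.

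**The case against.** The strongest reply is that the effect is tiny and its size is assumed. The other exclusions shrink f further, and a true IRR of 1 is not moved, so the null hypotheses in section 6 are not put at risk. All of that stands, and it limits the weight of the point. It does not remove the mismatch between rule and list.

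A second reply is that section 5 keeps the P203 methods unchanged apart from dropping the secondary analyses, and that three countries are already reported. A new code would break comparability. This is a real cost, which a sensitivity analysis on the present list can meet.

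A reader might also infer four stronger things that the documents do not support.

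- **That patients with a known meningioma enter 2B because of the missing code.** They enter because the baseline exclusion names malignant tumours only. Adding D32 would not change entry.
- **That omitting brain metastases contradicts the rules.** The protocol never calls metastases brain tumours. In Table 10, metastatic cancer has an arrow to seizures only and none to DL, and it is in none of the 19 adjustment sets in Table 11. The intention is unstated, so this calls for clarification.
- **That tumours of uncertain behaviour (D42, D43) are wrongly left out.** The rules promise benign and malignant tumours, and these are neither.
- **That tumours gather in reference time and push the IRR below mere dilution.** The model compares rates per person-time, with age and calendar year split and adjusted. No part of the protocol shows a higher adjusted tumour rate in reference time.

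**Conclusion.** The point holds for D32. The combined brain-tumour row in Annex 6 does not fully implement the 2B censoring rule or the same-hospitalization case exclusion, and some tumour-related first seizures coded R56 as primary diagnosis will stay in the outcome. The other filters reduce their number without removing them.

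The expected consequence is a small dilution of the seizure IRR towards 1. With an assumed share of 2% to 10%, 1.7 reads 1.69 to 1.63 and 1.5 reads 1.49 to 1.45. This rests on the assumed share and on tumour seizures being unrelated to DL timing after adjustment. No direction beyond dilution is shown. The status of C79.3 is an open question for the sponsor. The correction is worth making because it is cheap and brings the codes into line with the stated rule, not because the numbers would move much.

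**What to change.** - Add D32 to the combined malignant-and-benign brain-tumour row in Annex 6. Apply it in the 2B censoring (section 7.2.2) and the same-hospitalization exclusion (section 7.3.2) for all four countries.
- Keep the present list (C70, C71, D33) as a sensitivity analysis, so that the results can be set beside the P203 report.
- State whether brain metastases (C79.3) count as brain tumour. If they do, add the code to both tumour rows; this would then also change the 2A and 2B exclusions for malignant tumours. If they do not, say so.

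The cost is a slight loss of person-time, a small departure from the P203 code list, and a rerun of the 2B seizure analysis for the three countries already reported.
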